4.4 TERMINATION RULES

4.4.1 Criteria and procedures for prematurely terminating the study treatment

Several situations are possible

- Temporary suspension of treatment: the investigator must document the reason for suspending and resuming the treatment in the participant's source file and the case report form (CRF)
- Premature discontinuation of treatment, but the participant remains enrolled in the study until the end
 of their participation
- Premature discontinuation of treatment and withdrawal from the study

The investigator must:

- o Document the reason(s)
- o Collect the assessment criteria at the time of ending participation in the study, if the participant agrees
- o Schedule a follow-up for the participant, particularly in case of a serious adverse event.

In the case of severe adverse events, the investigator must notify the sponsor and follow up the participant for 1 month following the premature discontinuation of treatment. Notification of a serious adverse event must be sent by email ([contact]) to the sponsor. The serious adverse event will be monitored until it is resolved.

4.4.2 Criteria and procedure for premature withdrawal of a participant from the study

- Participants may exit the study at any time and for any reason.
- If, during the course of his/her participation in the study, the participant presents one of the following exclusion criteria, then the study product/procedure must be discontinued but the participant will continue to be monitored for the study.

List the relevant criteria

- Pregnancy;
- Expected death or withdrawal of life-sustaining treatments within 48 hours;
- Previously enrolled in this study, or in an other ineterventional study;
- Hypersensitivity to hydrocortisone or fludrocortisone or any of their excipients (SPC)
- Women of childbearing potential not using contraception
- Nursing women
- The investigator can temporarily or permanently withdraw a participant from the study for any safety reason or if it is in the participant's best interests.
- Participant lost to follow-up: the participant cannot be located. The investigator must make every effort to reconnect with the participant (and document his attempts in the source file), at least to determine whether the participant is alive or dead. In this study vital status will be searched for in the National Registry of Deaths thanks to their family and first name and their date of birth and their place of residence.

If a participant exits the study prematurely or withdraws consent, any data collected prior to the date of premature exit may still be used.

In case of premature exit from the study, this will in no way affect their usual care for their condition.

- In case of serious adverse events, see the corresponding section on vigilance

The case report form must list the various reasons why the participant has discontinued the study:

- □ Lack of efficacy
- □ Adverse reaction
- □ Another medical issue
- $\hfill\square$ Personal reasons of the participant
- □ Explicit withdrawal of consent
- □ Lost to follow-up

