4.4.3 Follow-up of participants following premature withdrawal from the study

If a participant discontinues the study, this will in no way affect their usual care for their condition. In the event of serious adverse events following premature discontinuation of treatment and participation of the patient in the study; see section 6.4.1

4.4.4 Procedures for replacing participants,

No replacement of participants is planned in this study.

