5.6 Early termination visit

Patients are allowed to withdraw their participation in the research at any time and for any reason. Patients included in the research (unable to consent or included by a relative) can refuse to continue their

participation after recovery.

The investigator can temporarily or permanently withdraw a participant from the study for any safety reason

or if it is in the participant's best interests.

If a participant wishes to withdraw their consent from the study, we will use the following strategies to minimize the impact on the validity of the trial meanwhile respecting the participant's right to withdraw. We will seek a better understanding of the patient's wishes and offer the following alternatives to complete withdrawal:

1) Discontinue in-person follow-up but allow telephone follow-up;

2) Discontinue in person and by telephone follow-up but allow access to medical records and to use personal data to be able to get life status from the national centre of epidemiology of deaths (Centre d'épidémiologie sur les causes de décés - Cépidc) via the SNDS (Système National des Données de Santé).

In any case, all the data that would have been collected before the patient's consent withdrawal will be kept in.

5.7 Expected length of participation and description of the chronology and duration of the study.

- Duration of enrolment period: 48 months

- Duration of participation for each participant: 6 months
 - o Treatment period:7 days

- o Duration of follow-up period:6 months
- Total study duration: 54 months
- Randomization (Interventional phase): will be performed after the inclusion visit, less than 24 hours after receiving the results of the biomarker.
- Follow-up duration and procedures for the participant in the event of premature discontinuation

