5.16 Cohort Retention

Once a patient is enrolled in the trial, the clinical site will make every reasonable effort to follow the participant for the entire duration of the study period. Loss to follow up is rare in critical care trials, especially for outcomes measured at day 90. To minimize loss to follow-up at 6 months, consent forms will encompass permission to collect alternate contacts information. If necessary, the URC HUPIFO team will request the assistance of the local research team who will have access to the participant medical records, and potentially information contact of the patient's treating general practicioner notably to document survival of the patient.

Participants may discontinue their participation to the RECORDS Trial at any time. If a participant wishes to withdraw their consent from the study, we will use the following strategies to minimize the impact on the validity of the trial meanwhile respecting the participant's right to withdraw. We will seek a better understanding of the patient's wishes and offer the following alternatives to complete withdrawal:

1) Discontinue in-person follow-up but allow telephone follow-up;

2) Discontinue in person and by telephone follow-up but allow access to medical records and to use personal data to be able to get life status from the national centre of epidemiology of deaths (Centre

d'épidémiologie sur les causes de décés - Cépidc) via the SNDS (Système National des Données de Santé).

In any case, all the data that would have been collected before the patient's consent withdrawal will be kept in.

We will adhere to the intention-to-treat principle and data from patients will be analyzed in the group to which they will have been allocated irrespective of protocol adherence. Reasons for protocol deviations, should they arise, will be recorded. In the special case of participants mistakenly randomized, we will only allow post-randomisation exclusions if: 1) the information about ineligibility was available at randomization; 2) two members of the Steering Committee agree that the participant was mistakenly randomized; 3) participants did not receive the intervention; and 4) participants remain blinded to their allocation.^{30,31}

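### Sections 4.4.2 and 5.6 let the investigator end study participation, not just treatment, for safety reasons, so non-fatal outcomes may be lost in patients selected by a safety event

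*Protocol*

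**What the plan says.** Section 4.4.1 lists several situations that may follow a stop of study drug. Two matter here: "Premature discontinuation of treatment, but the participant remains enrolled in the study until the end" and "Premature discontinuation of treatment and withdrawal from the study". It gives no criterion for choosing between them. After a severe adverse event, the investigator must "follow up the participant for 1 month following the premature discontinuation of treatment", and the event itself is tracked to resolution.

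Section 4.4.2 deals with two cases differently. If a listed exclusion criterion arises during the study, "the study product/procedure must be discontinued but the participant will continue to be monitored for the study". Separately, the investigator "can temporarily or permanently withdraw a participant from the study for any safety reason", or where this serves the participant's interests. Section 5.6 repeats that power. The CRF list in 4.4.2 of reasons for discontinuing the study puts lack of efficacy, adverse reaction and another medical issue beside consent withdrawal and loss to follow-up. For early exits, 4.4.2 mentions only data gathered before the exit as usable.

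Section 4.4.3 offers no outcome follow-up: "In the event of serious adverse events following premature discontinuation of treatment and participation of the patient in the study; see section 6.4.1". Section 6.4.1 is about data ownership. In 5.7 the line "Follow-up duration and procedures for the participant in the event of premature discontinuation" has nothing after it, although this may be a conversion loss and nothing here rests on it.

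Section 5.16 promises every reasonable effort to follow each patient for the whole study period, and that "data from patients will be analyzed in the group to which they will have been allocated irrespective of protocol adherence". Section 3 expects no missing data for the primary outcome.

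**The concern.** Stopping a drug and leaving a trial are different events. Only the first needs to follow from a safety problem. A patient whose drug is stopped, and who has not refused further contact, can still be assessed on schedule, and an intention-to-treat comparison needs those assessments. The protocol lets a site turn the first event into the second by its own decision, and the CRF list gives it a ready box to tick.

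Loss by this route would not be random. It is triggered by a safety event, so it depends on prognosis, and if the drug causes such events it also depends on arm. The primary outcome in 5.14.1 needs ventilation, vasopressor and SOFA status beyond day 28 as well as survival. Withdrawal during the 7-day treatment period could also cut short the 28-day vasopressor-free-day count that drives the sequential analyses in Section 9. An analysis plan can choose how to handle missing values, but it cannot restore observations that the protocol allowed a site not to make.

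**Working it through.** **1. Planned size and power.** Inputs from Section 9.1: 45% versus 35%, two-sided 5%, 80% power, 1:1. Unpooled formula: (1.960 + 0.842)² × (0.45×0.55 + 0.35×0.65) / 0.10² = 372.8, so 373 per arm, as stated. Power at 900 per arm is 99.16%, as stated. Losing 2%, 5% or 10% of patients leaves about 99.0%, 98.8% or 98.5% (pooled formula). Power is not the issue.

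**2. Calendar.** Treatment lasts at most 7 days (5.11.4). A stop on day 0 to 7 plus 30 days ends on day 30 to 37. If one month is a cap, 90 − 37 = 53 to 90 − 30 = 60 days before day 90 go unobserved. The day 7, 14 and 28 measures are covered even then.

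**3. What can be recovered after an investigator withdrawal.**

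| Item | Recoverable? |
|---|---|
| Death to day 90 | Largely. 5.14.1 uses hospital files and telephone calls; 6.4 and 11.4.4 provide for a national vital-status query for patients generally. The registry search in 4.4.2 is placed under loss to follow-up. |
| Serious adverse events | Largely. 7.3.2.4 keeps notification open to 90 days after treatment; 7.3.2.5 follows events after a patient has left. |
| The event that led to withdrawal | Yes. Data before exit are kept. |
| Ventilation, vasopressor and SOFA status after exit | Not assured. No registry holds them, and the reduced-follow-up options in 5.6 and 5.16 are offered when the participant withdraws consent. |
| Vasopressor-free days, if exit precedes day 28 | Not assured, for the same reason. |
| New non-serious events after exit | Not assured. |

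**4. Illustration of bias.** The protocol gives no withdrawal rate, so everything here is assumed: true failure rate p = 45% in both arms, and a fraction w withdrawn, higher on active treatment.

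(a) All withdrawn patients excluded, deaths included. With failure risk r among those withdrawn, the observed rate is (p − w·r)/(1 − w).
- r = 0.60: at 5% versus 2% withdrawn, 44.21% versus 44.69%, a false benefit of 0.48 points; at 10% versus 5%, 0.88 points.
- r = 0.90: 42.63% versus 44.08%, 1.45 points; at 10% versus 5%, 2.63 points, with two-sided rejection of 19.3%.
- r = 0.45: no bias.

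(b) Deaths retained, withdrawn survivors excluded. With death risk r_d and non-fatal failure risk r_n among those withdrawn, the observed rate is (p − w·r_n)/(1 − w(1 − r_d)).
- r_d = 0.35, r_n = 0.35: at 5%, 0.4325/0.9675 = 44.70%; at 2%, 0.4430/0.9870 = 44.88%. False benefit 0.18 points, against 0.81 under (a) with the same r = 0.70.
- r_d = 0.65, r_n = 0.10: at 5%, 0.4450/0.9825 = 45.29%; at 2%, 0.4480/0.9930 = 45.12%. False harm 0.18 points.

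Under (b) the bias is zero when r_n = p(1 − r_d), that is r_d = (r − p)/(1 − p). For r = 0.70, r_d = 0.25/0.55 = 0.455, or 65% of failures. For r = 0.80, r_d = 0.35/0.55 = 0.636, or 80% of failures. Above those shares the sign reverses. The protocol does not give the share of failures that are deaths; Section 9.1 even labels its 45% and 35% as day-90 mortality.

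**The case against.** The strongest reply is that the power to withdraw is a permission. Section 4.4.1 also offers staying enrolled to the end, the two bullets in 4.4.2 address different situations, and 5.16 asks for full follow-up. That stands: outcomes may be lost, and nothing says they must be.

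A reader might infer that the protocol ends follow-up at one month after a safety stop. The wording does not establish this. It is a duty placed on the investigator after a severe event and can equally be read as a minimum; it does not cancel scheduled assessments.

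A reader might also infer that the harm signal behind cohort closure is erased. That goes too far. A patient withdrawn because of a qualifying grade 3 or higher event has already had it, earlier data are kept, and serious events are followed after exit.

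Finally, a reader might infer that the arm with more adverse reactions is bound to look better. Calculation (a) gives that result only by discarding deaths that the protocol can largely recover. Calculation (b) shows that the effect shrinks and can change sign. Intention-to-treat is stated, and missing-data handling may be set out in an analysis plan that is not at hand.

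None of this answers the central point. The power covers study participation, needs no refusal by the patient, and leaves the non-fatal components without an assured source.

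**Conclusion.** The point holds in limited form. Sections 4.4.2 and 5.6, together with the CRF list, permit loss of the non-fatal day-90 components, vasopressor-free days and later non-serious events in patients selected by a safety event. That sits badly with 5.16 and Section 3. The one-month wording in 4.4.1 is ambiguous, and the cross-reference in 4.4.3 is wrong.

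The size and direction of any bias are not established. At assumed withdrawal of 5% versus 2%, the cases worked here range from 1.45 points of false benefit, if deaths are dropped and 90% of those withdrawn would have failed, to 0.18 points of false harm, if deaths are kept and dominate. Bias vanishes under (a) if those withdrawn have average risk. The case for change rests on a stated rule that allows avoidable, outcome-dependent loss and is cheap to repair. It does not rest on any one bias figure.

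**What to change.** - **4.4.2 and 5.6:** limit the investigator's decision to study treatment. State that follow-up ends only when the participant or representative refuses it, after the reduced options already in 5.6 (telephone only, or records and vital status only) have been offered.
- **4.4.1:** state that one month is a minimum for following the event and that scheduled assessments to day 90 and 6 months continue.
- **All early exits:** apply vital-status retrieval and medical-record access to each, unless the participant refuses.
- **eCRF:** use one list for stopping treatment (adverse reaction, lack of efficacy, other medical issue) and another for leaving the study (consent withdrawn, lost to follow-up).
- **4.4.3:** correct the cross-reference.

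When treatment should be stopped is a clinical matter and is not addressed here.

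The cost is protocol wording, one eCRF page and some extra follow-up of patients off treatment. No new visits are needed, since these patients are already scheduled to 6 months. The change also removes the investigator's power to end follow-up on best-interest grounds; the reduced options would have to serve in such cases.

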4.4.3 Follow-up of participants following premature withdrawal from the study

If a participant discontinues the study, this will in no way affect their usual care for their condition. In the event of serious adverse events following premature discontinuation of treatment and participation of the patient in the study; see section 6.4.1

4.4.4 Procedures for replacing participants,

No replacement of participants is planned in this study.

4.4.5 Full or partial discontinuation of the study

AP-HP as sponsor or the Competent Authority (ANSM) can prematurely discontinue all or part of the study, temporarily or permanently, in the following situations:

 first of all, if suspected unexpected serious adverse reactions (SUSARs) are observed in one of the treatment arms or if there is a discrepancy in the serious adverse reactions between the treatment arms, requiring a reassessment of the benefit-risk ratio for the study

- if an interim analysis confirms the efficacy of one of the treatment arms or, alternatively, the lack of efficacy

However these situations are unlikely to occur as this trial is an adaptive multi arm trial that will, per essence, stop the arms that show patients with increased risk of toxicity or of a lack of efficacy.

Similarly, AP-HP, as the sponsor, or the Competent Authority (ANSM) may decide to prematurely discontinue the study due to unforeseen issues or new information about the product, in light of which the objectives of the study or clinical programme are unlikely to be achieved.

AP-HP as sponsor reserves the right to permanently suspend enrolment at any time if it appears that the inclusion objectives are not met.

In all cases in which a study is discontinued, this will in no way affect participants currently enrolled in the study that will benefit from usual care for their condition. Notably, the participants included in the study must be monitored until the end of their participation, as set forth in the protocol.

If the study is prematurely discontinued for safety reasons, the decision and justification will be provided by the sponsor (AP-HP) to the Competent Authority (ANSM) and to the CPP (Research Ethics Committee) within a period of 15 days.

4.5 Randomization Methods

4.5.1 Allocation sequence generation

[figure not shown]
A computer process will be used to generate allocation sequences in a 1:1. Any evidence suggesting increased harm in patients presenting with a contemplated biomarker will lead to the termination of recruitment of patients presenting with this biomarker and will qualify the corresponding biomarker for identifying patients who should not be treated by hydrocortisone plus fludrocortisone (see section 9). A randomization list will be generated beforehand by a computer program and verified according to the procedures of the sponsor, independently from the physicians who will recruit patients.

4.5.2 Stratification:

Randomization will be stratified on the following biomarkers:

- 1. CIRCI
- 2. Endocan
- 3. GILZ
- 4. CPD
- 5. Transcriptomic SRS2
- 6. Endotype B
- 7. COVID-19
- 8. Influenza
- 9. Other respiratory viruses

The full statistical analysis plan will be published before the first interim analyse.

According to the adaptive design of the umbrella trial, the number of biomarker strata is not fixed and will vary with 1) information gained from actual study participants on added-value of a specific biomarker, 2) from new biomarker released by RECORDS WP3-6, 3° from new relevant biomarker released in the literature that will be screened n a trimester basis throughout the study period. These novel biomarkers may include new clinical algorithm or phenotypes, new omic-derived signature, new biological biomarker issued from blood, urine or exhaled air.

4.5.3 Implementation

Randomization will be performed after the inclusion visit by ICU physicians, less than 24 hours after receiving the results of the biomarker.

Randomization will be centralized and performed with an internet-centralized service running 24/7 using the CleanWeb software, also used for the electronic Case Report Form (eCRF) (cf. infra).

4.6 BLINDING

Intensivists, research personnel, ICU personnel, participants, members of the Executive and Steering Committees, and the data analyst will be blinded to the treatment allocation.

Only the pharmacist, from the General Agency of Equipments and Health Products of The Paris Public Hospital Assistance (AGEPS - APHP) will be unblinded. Treatments will be available in the pharmacies of the participating centers 24 hours a day, 7 days a week. Blinding will not be compromised because treatment boxes will be numbered, and randomization will assign a kit number present in the center.

4.7 UNBLINDING PROCEDURES

Treatment will be unblinded in case of suspected unexpected Serious Adverse Event (SAE), in the situation where the clinical condition of the patient warrants knowing whether or not he/she received hydrocortisone or fludrocortisone.

In practice, unblinding will be requested for any reason considered essential by the investigating physician by calling upon:

- In situations requiring unblinding in an emergency : (in case of suspected unexpected Serious Adverse Event (SAE), in the situation where the clinical condition of the patient warrants knowing whether or not he/she received hydrocortisone or fludrocortisone) at the poison control centre at Fernand Widal Hospital, [contact].

- Apart from an emergency situation at the DRCI (Clinical Research and Innovation Department) to the DRCI project advisor whose contact informations are listed on the protocol cover page

5 IMPLEMENTATION OF THE STUDY

Before any examination or intervention related to the study may be carried out, the investigator must obtain the *freely given, informed and written consent of the participant, or of his/her legal representative.*

Individuals liable to participate in studies stipulated in line 1° of article L. 1121-1 of the *Code de la Santé Publique* (French Public Health Code) benefit from a preliminary medical examination adapted to the study.

The study will be conducted in two phases: an observational phase and an interventional phase.

5.1 RUN-IN observational period

The observational phase (Run in period) lasts at least 6 months. Its aim is to collect as much information as possible on biomarkers likely to influence responses to corticosteroids under the usual conditions of care and develop reference values for the biomarkers. These values will later be used during the second phase (interventional phase) to set up diagnostic tests in order to rapidly identify patients with sepsis who may be sensitive or resistant to corticoids

During the first stage, run-in observational period, all participants will receive as a standard of care, openlabeled, commercialized hydrocortisone and fludrocortisone, or dexamethasone or methylprednisolone, at equivalent doses, or no corticosteroids as left at physician discretion. Hydrocortisone will be given as a 50mg intravenous bolus every 6 hours (equivalent to 6 to 8 mg once daily of dexamethasone, equivalent o 40 mg per day of continuous infusion of methylprednisolone) for seven days and fludrocortisone will be given orally/enteraly as a 50μ g tablet once a day (in the morning) for seven days.

All consecutive eligible patients should be approached for participation in the run-in observational part of the study by the clinical investigators or person qualified to carry out the research. The clinical investigator will inform the eligible person of this study then collect the consent of this person to use his/her clinical data and biological samples routinely collected for the present research. If the patient is unable to confirm or not his/her consent within the time window allowed by the protocol, his or her authorized persons (members family, curator, guardianship, trusted person) may be approached in person. The local research team could also enroll eligible patients.

